8.1.1. Primary Analysis

The primary efficacy analysis will be performed on the mITT set at the TOC visit and will compare the proportion of subjects, in the treatment and placebo groups, who have a clinical cure at the TOC visit.

The number and percentage of subjects with clinical cure at the TOC visit will be presented by treatment group. A Cochran Mantel Haenszel (CMH) test adjusted for site and diabetes mellitus diagnosis (Yes or No) will be performed to assess the statistical significance of a difference between treatment groups in the primary efficacy analysis. Mathematically stated:

$$\begin{aligned} H_0: \text{TOC Clinical Cure Rate Oral ibrexafungerp 300-mg dose} &= \text{TOC Clinical Cure Rate Placebo} \\ H_1: \text{TOC Clinical Cure Rate Oral ibrexafungerp 300-mg dose} &\neq \text{TOC Clinical Cure Rate Placebo} \end{aligned}$$

The p-value, odds ratio and 95% confidence interval will be presented in the ibrexafungerp 300-mg treatment arm compared to the placebo arm. Missing data for clinical outcome will be imputed using the NRI method described in Section 4.4. Additional summarizations will be performed by Candida Species of the baseline yeast, and the same inferential analysis will be performed, as appropriate.

The same inferential analysis employing the same methods as for the primary analysis will be performed for the ITT set and PP set to assess clinical cure at TOC visit. Missing data for clinical outcome will be imputed using the NRI method described in Section 4.4. No adjustment of type I error will be performed as these analyses are considered supportive to the primary analysis.

A sensitivity analysis using the mITT set will be performed where subjects with the imputed clinical outcome using the NRI method at TOC visit will be removed from the analysis.

Two subgroup analyses will be performed depending on Body Mass Index category ($\leq 35 \text{ kg/m}^2$ or $> 35 \text{ kg/m}^2$).

Analysis of time to resolution of signs and symptoms after initiation of study drug will use Kaplan-Meier method to estimate the median resolution time and its 2-sided 95% confidence intervals (CIs) based on the ITT, mITT, and PP sets. The time to resolution of signs and symptoms after initiation of study drug is defined as time (days) from first dose of study medication to the first resolution of signs and symptoms. Subjects who discontinued early will be censored at the last available assessment.

Kaplan-Meier curves for time to resolution of signs and symptoms after initiation of study drug will be provided by treatment group based on the ITT, mITT, and PP sets.

Summary of the number and percentage of subjects with continued clinical response at the Follow-up (FU) visit, which defined as continued absence of signs and symptoms in subjects who achieved Clinical Cure at the TOC visit, will be provided by treatment based on the ITT, mITT, and PP sets.

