11.1 Inclusion Criteria

Subjects must fulfill all of the following criteria to be eligible for study admission:

1. Subject is a postmenarchal female subject 12 years and older and is in good general health based on medical history, physical examination, vital sign measurements and safety laboratory tests performed at the Screening visit and/or prior to administration of the initial dose of study drug.
2. Subject has a diagnosis of symptomatic AVVC that meets the following criteria:
 - a. Minimum composite vulvovaginal signs and symptoms score of ≥ 4 with at least 2 signs or symptoms having a score of 2 (moderate) or greater in the VSS Scale at Baseline
 - b. Positive microscopic examination with 10% KOH in a vaginal sample collected at Screening revealing yeast forms (hyphae/pseudohyphae) or budding yeasts
 - c. Normal vaginal pH (≤ 4.5)
3. Subject is able to take oral tablets.
4. Subject is not pregnant or lactating and is highly unlikely to become pregnant since she meets at least one of the following criteria:
 - a. Subject is a female subject who is not of reproductive potential and is eligible without requiring the use of contraception. A female subject who is not of reproductive potential is defined as one who: (1) has reached natural menopause (defined as 6 months of spontaneous amenorrhea with serum follicle-stimulating hormone levels in the postmenopausal range as determined by the local laboratory, or 12 months of spontaneous amenorrhea); (2) has undergone bilateral oophorectomy and/or hysterectomy or (3) is 3 months post bilateral tubal ligation. Spontaneous amenorrhea does not include cases for which there is an underlying disease that causes amenorrhea (e.g. anorexia nervosa).

- b. Subject is a female subject who is of reproductive potential and is using an effective contraceptive method including intrauterine device, hormonal contraceptives (i.e., vaginal ring, implant, oral, injectable or patch) for at least 30 days before baseline, and agrees to continue using the contraceptive method through at least 10 days after the completion of study therapy. Vasectomy in the male partner is also an acceptable contraceptive method as long as performed at least 3 months prior to Baseline.

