Unless otherwise specified, baseline will be defined as the last non-missing assessment prior to or on the date (and time if appropriate) of the first dose of study drug. Change from baseline is defined as: post-baseline value – baseline value.

The study day will be calculated as follows:

If the assessment date occurs on or after the date of the first dose of study drug:

$$\text{Study day} = \text{assessment date} - \text{first dose date} + 1.$$

If the date of interest occurs before the date of the first dose of study drug:

$$\text{Study day} = \text{assessment date} - \text{first dose date}$$

There is no study day 0.

All analyses will be conducted using SAS Version 9.3 or higher. All statistical tests will be two-sided and interpreted at a 5% significance level.

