4.1. Sample Size

The primary endpoint of the study is the percentage of subjects achieving a clinical cure at the TOC visit. Assuming clinical cure rates of 50% and 30% for ibrexafungerp and placebo administered in a 2:1 ratio, respectively, approximately 282 subjects will provide 90% power to detect a difference between ibrexafungerp and placebo based on a Pearson’s Chi-squared test with a Type 1 error rate of 5%. Because it is expected that approximately 20% of subjects may not have a mycological culture-confirmed infection at Baseline and approximately 10% may withdraw early

from the study, an additional 84 subjects are added for a total of 366 subjects (244 subjects randomized to ibrexafungerp and 122 subjects, to placebo).

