8.2.5. Composite Score of the Vulvovaginal Signs and Symptoms

The following secondary efficacy endpoints will be analyzed using an analysis of covariance (ANCOVA) model having treatment group, site and diabetes mellitus diagnosis (Yes or No) as classification variables, and the baseline value as the continuous covariate.

- The change in signs and symptoms score from Baseline to TOC visit;
- The change in signs and symptoms score from Baseline to FU visit.

For each treatment and treatment comparison versus placebo, the least squares mean, associate standard error (SE), 95% confidence interval and corresponding p-value will be presented.

A descriptive summary will be presented for the followings based on the mITT and PP sets:

- The change in total sign score from baseline to TOC and FU visits;
- The change in total symptom score from baseline to TOC and FU visits;
- The change in signs and symptoms score from TOC to FU visit.

A listing will be provided to present the signs and symptoms score and mycological outcome for all subjects in the ITT set. Assessments that are not done will be presented in the data listing with a missing value.

9. Safety Analysis

Safety analyses will be performed on all subjects in the safety set. Analyses will be based on adverse events, vital signs, clinical laboratory assessments, and physical examination findings. Safety analyses in general will be descriptive and will be presented in tabular format with the appropriate summary statistics by treatment group.

Individual subject listings will be provided to support the tables.

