9.5. Vaginal Samples – pH, KOH and Other Pathogen Results

Vaginal samples will be obtained for pH testing, KOH testing, fungal culture, and other pathogens (Chlamydia, Gonorrhea, and Herpes) at the screening visit and other times during the study when persistence or recurrence of vulvovaginal symptoms occurs. Subjects with other pathogens other than Candida, suspected at screening will be excluded from the study.

The pH testing results will be summarized descriptively at the scheduled post-baseline visits by treatment group.

The KOH testing results will be classified as Positive (Yeast Only), Positive (Yeast and other pathogens), Negative (Yeast and other pathogens), and Positive (Other pathogens only). This categorical data will be summarized with the frequency and percentage of subjects at the scheduled post-baseline visits by treatment group.

The proportion of subjects with Chlamydia, Gonorrhea, and Herpes will be summarized at the scheduled visits by treatment group.

All by-subject vaginal sample testing data will be presented in a listing.

10. Interim Analysis

No interim analysis is planned for this study.

11. Changes in the Planned Analysis

The following have changed from the protocol:

- For the secondary efficacy endpoint “Change from Baseline in Composite Score of the Vulvovaginal Signs and Symptoms” described in Section 8.2.5, an analysis of covariance (ANCOVA) model is recommended rather than a two-way ANOVA model. Baseline value will be considered as possible contributor to any observed differences. Additionally, other variables may be considered during blinded data review.
- Add the randomization stratification factor, diabetes mellitus diagnosis (Yes or No), as justification factor in the efficacy analyses models.

12. References

Sobel, JD. Vaginal candidosis. *Lancet* 2007; 369:1961–71.

William G. Cochran (December 1954). "Some Methods for Strengthening the Common χ^2 Tests". *Biometrics*. 10 (4): 417–451.

Gelman, Andrew (February 2005). "Analysis of variance? why it is more important than ever". *The Annals of Statistics*. 33 (1): 1–53.

13. Appendices

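### The primary analysis of clinical cure leaves out the baseline signs-and-symptoms score; the planned test is valid, but a modest and nearly free gain in precision is missed

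*SAP*

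**What the plan says.** The primary test in SAP 8.1.1 is described as follows: "A Cochran Mantel Haenszel (CMH) test adjusted for site and diabetes mellitus diagnosis (Yes or No) will be performed". Protocol 18.6.2 adjusts for site only. The ITT and PP analyses of cure repeat the primary method, and the sensitivity analysis that removes imputed outcomes adds no covariate. SAP 8.2.1 to 8.2.4 carry the same method over to the binary secondary endpoints.

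The change in composite score is handled differently. SAP 8.2.5 uses ANCOVA with treatment, site and diabetes, "and the baseline value as the continuous covariate". SAP section 11 gives the reason for moving away from the protocol's ANOVA: "Baseline value will be considered as possible contributor to any observed differences". It also allows further variables to be considered at blinded data review, but that remark sits in the change-score item and names no covariate for cure.

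The score exists for every eligible woman. Protocol 11.1 requires a composite of at least 4, "with at least 2 signs or symptoms having a score of 2 (moderate) or greater", and SAP 8.1 gives a maximum of 18. SAP 8.1 defines cure as a score of 0 on every sign and symptom, with no additional antifungal or topical vaginal treatment.

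SAP 4.1 sizes the trial without covariates: "Assuming clinical cure rates of 50% and 30% for ibrexafungerp and placebo administered in a 2:1 ratio", "approximately 282 subjects will provide 90% power to detect a difference between ibrexafungerp and placebo", using a Pearson chi-squared test. SAP section 4 adds: "All statistical tests will be two-sided and interpreted at a 5% significance level".

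**The concern.** A woman who starts at 4 has less far to go to reach zero than one who starts at 15, so the starting score is a natural candidate predictor of cure. It is measured before treatment and needs no new data. Adjusting a randomised comparison for a prognostic baseline variable narrows the confidence interval, and the SAP accepts that logic for a secondary endpoint but not for the primary one. The placebo arm is small: 94 women in the sample-size calculation and about 98 in the expected mITT set (366 × 0.8 / 3). What is at stake is some power and some width of the confidence interval on the main result.

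**Working it through.** **1. Reproduce the plan's figure.** Inputs from SAP 4.1 and section 4: 30% and 50% cure, 2:1 allocation, two-sided 5%, 90% power. The pooled rate is (0.30 + 2 × 0.50)/3 = 0.4333, with variance 0.2456.

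Placebo n = [1.960 × √(1.5 × 0.2456) + 1.2816 × √(0.21 + 0.25/2)]² / 0.20² = (1.1895 + 0.7418)² / 0.04 = 93.2, rounded up to 94. The total is 3 × 94 = 282, as stated, with power 90.2%. The design therefore does not rely on covariate adjustment.

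**2. What adjustment could add, by formula.** Let R² be the share of within-arm variance in cure explained by the baseline score. The adjusted variance is the unadjusted variance × (1 − R²). At 188 vs 94 the unadjusted 95% CI half-width is 1.96 × √(0.25/188 + 0.21/94) = 11.7 points. R² is not in the documents, so a range is shown.

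| R² (assumed) | Power at 282 | CI half-width (points) | N for the planned power, 282 × (1 − R²) |
|---|---|---|---|
| 0 | 90.2% | 11.7 | 282 |
| 0.02 | 90.8% | 11.6 | 277 |
| 0.05 | 91.7% | 11.4 | 268 |
| 0.10 | 93.0% | 11.1 | 254 |
| 0.15 | 94.3% | 10.8 | 240 |

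**3. Simulation at 188 vs 94.** Assumptions: baseline score with mean about 9 and SD about 2.6, kept within 4 to 18; 8% diabetic; 30 sites with no site effect. There were 2,000 to 4,000 trials per setting, and the simulation error of one power figure is about √(0.9 × 0.1/3000) = 0.5 point.

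- Planned CMH by site × diabetes: about 84-86%.
- CMH by diabetes alone: about 90% (sets ranged from 89% to 91.2%).
- Logistic model with diabetes and the continuous score, by odds ratio for cure per SD of score:
  - 0.61 (R² about 0.05): 91.3-91.4%
  - 0.50 (R² about 0.09): 92.6-92.7%
  - 0.41 (R² about 0.14): 93.9-94.1%

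A smaller set of 2,000 trials gave 90-92% for odds ratios of 0.61 to 0.50. Against about 90%, the score is worth about 1, 2 to 3, and up to 4 points, in line with step 2.

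CMH by diabetes × four severity bands, compared with diabetes alone, changed power by −0.5 point at 0.8, +0.2 at 0.67, +0.9 at 0.61, +2.1 at 0.50 and +2.7 at 0.41. The first two are within simulation error.

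**4. Simulation of the standardised difference.** This used the expected mITT set (366 × 0.8 = 293), unequal sites with a site SD of 0.3 on the logit scale, a baseline mean of 9.5 and SD of 2.8 before limiting to 4-18, and blocks of 6 within diabetes strata. Adding the score to diabetes moved power from 89.9% to 90.8% at an odds ratio of 0.80, from 91.3% to 92.1% at 0.67, and from 91.2% to 92.6% at 0.50. Variance fell by 1%, 3% and 9%. The gain of 1.4 points at 0.50 is below the 2 to 3 in step 3, so that figure is approximate. In the null scenario run, type I error was 5.2%, against 5.5% for the planned CMH.

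**5. Separating the site effect.** The step from about 84-86% to about 90% in step 3 comes from removing about 30 × 2 = 60 strata, with no use of the score. With true site SDs of 0.3 and 0.6 on the logit scale, the planned test reached 84.7-87.9% and the logistic model without site 89.5-93.5%. The part due to site strata was then 2 to 5 points.

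**6. Adding the score on top of site × diabetes.** Splitting each stratum by a two-level score lowered power from 85.0-86.5% to 82.0-84.1% in the step 4 set-up.

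**The case against.** The strongest reply is that nothing here is wrong. The CMH test is valid, the sample size assumes no covariate, and adjusting for the randomisation factor and for the site named in the protocol is conventional. All of that stands.

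The contrast with SAP 8.2.5 is also weaker than it looks. A change score contains the baseline value by construction, so there is a specific reason to adjust it, whereas cure is an absolute state at one visit. Treating the two differently is defensible. The case for adjusting cure rests on plausible prediction and low cost, not on an inconsistency.

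The gain is unproven as well. Neither document relates the score to cure, and a weak predictor adds nothing that can be told apart from simulation error.

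A reader might infer that chance imbalance in severity biases the planned result. It does not. With 188 and 94 women, the standard error of the baseline difference is √(1/188 + 1/94) = 0.126 SD. An imbalance above 0.2 SD therefore arises in about 11% of trials, and the test's type I error and confidence interval already allow for it.

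A reader might also set about 85% beside 91-94% and credit the whole gap to the missing score. Step 5 of the working shows that most of it belongs to the site strata.

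**Conclusion.** The point holds as a modest missed efficiency in a valid analysis. Against adjustment for diabetes alone, the baseline score is worth about 0 points of power at an odds ratio per SD of 0.8 or nearer 1, about 1 at 0.61, about 2 to 3 at 0.50 and up to about 4 at 0.41. At R² of 0.10 the CI half-width falls from 11.7 to 11.1 points.

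These figures rest on assumed values for the score's distribution, its link with cure, the diabetic share and the site pattern. The documents supply only the cure rates, allocation, sample size, block size, score range and approximate number of sites. The shortfall of about 5 points from site × diabetes stratification (2 to 5 if sites truly differ) is a separate issue.

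It might also be inferred that every binary endpoint should be adjusted in this way. The documents give no reason to expect symptom severity to predict culture results, so the point does not extend to mycological eradication.

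**What to change.** Before unblinding, make these changes to the SAP:

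- **Model (8.1.1).** Pre-specify a logistic regression of clinical cure on treatment, diabetes and the continuous baseline composite. Name the standardised (marginal) difference in cure rates, with 95% CI, as the target estimate. The model's odds ratio is conditional on the covariates and differs from the marginal one.
- **No extra stratum.** Do not add severity to the site × diabetes CMH, because that lowers power.
- **Baseline definition.** Use the last complete composite before the first dose. At present SAP section 4 accepts values on the date of first dose while Protocol 18.3 requires them before it. Diary symptom ratings start on Day 1, and signs are rated at Screening.
- **Other endpoints.** Apply the same model to clinical improvement (8.2.4) and symptom resolution (8.2.3), whose outcomes lie on the same scale. Leave mycological eradication (8.2.1) out of this change.
- **Record (section 11).** State that the model replaces the CMH. Because it drops the site adjustment in Protocol 18.6.2, justify that separately and do not count its effect as a gain from the score.

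The cost is SAP wording and programming, with no new data, visits or subjects. The downside is that nothing is gained if the score does not predict cure.

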11.4 Early Termination

With effective oral therapy, immediate relief of all symptoms is not expected and subjects should not expect immediate relief.

If the subject experiences persistence or worsening or recurrence of symptoms that per the investigator's assessment (e.g., symptoms ≥ 3) warrant the use of rescue antifungal therapy, a vaginal examination with investigator's rating of signs should be completed. Additionally, vulvovaginal samples should be obtained for KOH testing and pH measurements by the local laboratory, fungal culture by the central laboratory and investigation of other pathogens such as bacterial vaginosis and *Trichomonas vaginalis* by the local laboratory.

If the KOH test is negative, the investigator should consider other causes for the persistence or worsening of the symptoms as antifungal rescue medication may not be indicated.

If the investigator's rating of the vulvovaginal signs and vaginal sample collection is not possible prior to the initiation of the rescue therapy, it should still be completed as soon as possible after rescue therapy is initiated.

In addition to the vaginal examination, the symptoms that led to the use of rescue antifungal therapy should be documented in the eCRF and the following procedures should also be completed:

- If rescue therapy is administered prior to or at the TOC visit, all TOC visit procedures should be completed and no additional visits will be needed. The subject will be considered as early termination due to lack of efficacy prior to or at TOC.
- If rescue therapy is administered after the TOC visit but prior to or at the FU visit, all FU visit procedures should be completed and no additional visits will be needed. The subject will be considered as early termination due to lack of efficacy after TOC but prior to or at FU.

Oral fluconazole [one 150-mg dose] may be provided to study sites as rescue medication. However, at the investigator's discretion other approved antifungal agent may be administered as rescue medication to a particular patient for whom fluconazole is not considered the optimal option. All rescue antifungal medications should be documented in the eCRF.

Details of study treatment groups and dietary requirements for treatment administration are provided in [Section 12.1](#) and [Section 12.2](#), respectively.

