5.1. Disposition

A disposition of subjects includes the number and percentage of subjects for the following categories: subjects in each analysis set (ITT, mITT, PP, SS), subjects who completed TOC visit, subjects who completed the study (without need for antifungal treatment), subjects who completed the study (with need for antifungal treatment at FU visit), subjects who discontinued from the study, and the reasons for study discontinuation will be presented by the ITT and mITT sets. All percentages will be based on the number of subjects in each corresponding set.

The reason for study discontinuation may include any of the following: lack of efficacy and/or use of antifungal therapy prior to TOC; use of antifungal therapy after TOC (but prior to FU visit); adverse event; lack of efficacy after TOC; lost to follow-up; physician decision; pregnancy; study terminated by sponsor; study subject withdrawal by parent or guardian; withdrawal by subject; other; death, and trial screen failure.

Subject disposition data will be presented in a listing.

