8.1. Primary Endpoint

The primary efficacy endpoint is defined as the proportion of mITT subjects who have a clinical cure (complete resolution of signs and symptoms) at the test-of-cure (TOC) visit.

Clinical outcomes will be assessed at the TOC Visit (Day 11) according to the following definitions:

- Clinical cure: Complete resolution of signs and symptoms of vulvovaginal infection without need for further antifungal treatment and topical vaginal drug therapy for the treatment of vulvovaginal irritation/pruritus prior to or at the TOC visit. Specifically, for complete resolution, any sign or symptom should be absent (score = 0);
- Clinical failure: No response to therapy or incomplete resolution of signs and symptoms or use of additional vulvovaginal or systemic antifungal therapy or topical vaginal drug therapy for the treatment of vulvovaginal irritation/pruritus prior to or at the TOC visit. For the subject who early terminated before TOC visit and received additional vulvovaginal or systemic antifungal therapy or topical vaginal drug therapy for the treatment of vulvovaginal irritation/pruritus prior to or at the early termination visit, the subject is considered a clinical failure.

Signs of VVC will be defined as the presence of erythema, edema, or excoriation. Symptoms of VVC will be defined as itching, burning, or irritation.

Each vulvovaginal sign will be objectively scored based on severity as follows:

- 0 = none (complete absence of any signs or symptoms);
- 1 = mild (slight);
- 2 = moderate (definitely present);
- 3 = severe (marked, intense).

Each vulvovaginal symptom will be objectively scored based on severity as follows:

- 0 = none (I have no discomfort);
- 1 = mild (I have some discomfort, but it does not bother me much);
- 2 = moderate (I have discomfort, which is annoying, but not enough to affect what I am doing);
- 3 = severe (I have discomfort, which is annoying enough to affect what I am doing).

The composite score of the vulvovaginal signs and symptoms will be calculated according to the following rules and this scale has a total possible score of 18.

- If all items of the vulvovaginal signs and symptoms have been scored, the composite score is calculated as the sum of the individual scores of all 3 items of signs and 3 items of symptoms;
- If any sign or symptom is not done, the composite score will not be calculated and treated as a missing data except at FU visit;

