- Subjects who are free of symptoms are not required per protocol to have a vaginal examination at FU visit, therefore signs are not considered missing. For subjects who do not present symptoms and have no sign rated at the FU visit, the composite score of the vulvovaginal signs and symptoms at the FU visit will be calculated as zero.

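### The Kaplan-Meier time to resolution in SAP 8.1.1 times visits rather than relief, and it leaves the handling of non-resolvers and rescued women unsettled

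*SAP*

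**What the plan says.** **Event and censoring.** SAP 8.1.1 states: "The time to resolution of signs and symptoms after initiation of study drug is defined as time (days) from first dose" to first resolution. It asks for a median with 95% confidence interval and for curves by arm in the ITT, mITT and PP sets. Its only censoring rule is "Subjects who discontinued early will be censored at the last available assessment".

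**When signs are rated.** Protocol 14.11 has the investigator rate signs at Screening and TOC, at FU only if the woman has symptoms, and at unscheduled visits if needed. The diary (Protocol 14.15) records symptoms daily from Day 1 to TOC, but no signs. SAP 8.1 adds: "If any sign or symptom is not done, the composite score will not be calculated". The exception is a symptom-free, unexamined woman at FU, for whom "the composite score of the vulvovaginal signs and symptoms at the FU visit will be calculated as zero".

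**Rescue.** Protocol 11.4 treats rescue up to and including TOC as early termination for lack of efficacy. Of later rescue it says: "The subject will be considered as early termination due to lack of efficacy after TOC but prior to or at FU". SAP 5.1 lists among its discontinuation reasons "lack of efficacy and/or use of antifungal therapy prior to TOC; use of antifungal therapy after TOC (but prior to FU visit". SAP 8.1 includes in clinical failure "No response to therapy or incomplete resolution of signs and symptoms or use of additional vulvovaginal or systemic antifungal therapy". SAP 8.2.1, 8.2.3 and 8.2.4 likewise count rescue within their windows as persistence or no improvement.

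**The concern.** A median time to resolution, printed with a confidence interval and a curve, will be read as how fast the drug brings relief. If the event can be recorded only at two visits, the number describes the appointment schedule.

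Two further gaps affect the height of the curve. Completers who never resolve have no stated censoring time. Women rescued for lack of efficacy seem to fall under the early-discontinuation rule, and Kaplan-Meier then treats them as likely to resolve later at the same rate as those still followed. Rescue signals that treatment has not worked, so that censoring is informative. It also conflicts with how the same women are classed in the responder outcomes.

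**Working it through.** **Inputs from the documents.** TOC is Day 11 ± 3 and FU is Day 25 ± 4 (SAP 3.1), giving Days 8-14 and 21-29. Cure at TOC is 50% on active and 30% on placebo (SAP 4.1). The active mITT set is about 244 × 0.80 = 195 (SAP 4.1: 244 randomised, 20% without culture confirmation). The SAP states no figure for this analysis. Its sample size does reproduce: 94 + 188 = 282, power 90.2%.

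**Assumptions.** Attendance is uniform within each window. A share q of women unresolved and unrescued at TOC resolve by FU (30% unless varied). The documents give no placebo rescue rate. The only rescue counts are from the Phase 2b study (Protocol 7.1): one woman on the 600-mg dose and seven on fluconazole.

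**1. The median.** With a share c resolved by TOC and no earlier censoring, the curve on Day d (8 to 14) is c × (d − 7)/7. The true day of resolution does not enter.
- c = 0.60: Day 12 gives 0.60 × 5/7 = 0.429 and Day 13 gives 0.60 × 6/7 = 0.514, so the median is Day 13.
- In 1,000 simulated trials of 195 women, the median was Day 13 (5th-95th percentile 13-14) both when TOC resolvers truly resolved on Days 1-4 (true median Day 4) and when they did so on Days 5-8 (true median Day 8).
- c = 0.50: the curve reaches exactly 0.50 on Day 14. In simulation the median fell at or before Day 14 in about half of trials and at Day 21 or later in the rest.

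**2. Completers who never resolve.** Suppose each is censored at her own FU day. On the k-th of the nine FU days, the women still at risk are those whose visit falls on that day or later, so the hazard is q/(10 − k). The unresolved share at the end is (1 − c) × ∏(1 − q/j), j = 1 to 9.
- Placebo, q = 0.30, no rescue: the product is 0.394, and the curve ends at 1 − 0.70 × 0.394 = 0.724. Truth is 0.30 + 0.70 × 0.30 = 0.51.
- q = 0.15: 1 − 0.70 × 0.642 = 0.551, against 0.30 + 0.70 × 0.15 = 0.405.

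**3. Rescued women censored.** With a share b rescued and censored before TOC, the curve at Day 14 reads c/(1 − b).
- Placebo, b = 10%: 0.30/0.90 = 0.333 instead of 0.30. With b = 5% it is 0.316, and with b = 30% it is 0.429.
- With a further 10% rescued at or after TOC, the curve ends at about 1 − (1 − 0.333) × 0.394 = 0.737, against a truth of 0.30 + 0.50 × 0.30 = 0.45. The overstatement is about 29 points, compared with about 21 with no rescue. Most of it comes from step 2.

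**4. Effect on the arm difference.** The true gap at Day 14 is 20 points.
- Rescue before TOC of 10% in both arms reads 0.556 − 0.333 = 22.2 points, which is wider.
- 5% on active and 10% on placebo reads 0.526 − 0.333 = 19.3 points, which is narrower.
- At the end of the curve, 10% in both arms reads [1 − 0.444 × 0.394] − 0.737 = about 9 points. Truth is (0.50 + 0.40 × 0.30) − (0.30 + 0.60 × 0.30) = 14 points, so the gap is narrower.

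The sign depends on the rescue rates and on the day at which the curve is read.

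**5. Is rescue really censored?** SAP 8.1.1 does not mention rescue. Protocol 11.4 makes rescued women early terminations, SAP 5.1 lists antifungal use before TOC, and between TOC and FU, as discontinuation reasons, and SAP 8.1.1 censors early discontinuations. Read together, they are censored. However, the event has no condition excluding rescue, and Protocol 11.4 has the TOC or FU procedures completed in rescued women. A zero score after rescue could therefore count as resolution.

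**The case against.** The strongest reply is that little depends on this analysis. It is not a listed endpoint (SAP 3.2), has no between-arm test and does not touch the primary Cochran-Mantel-Haenszel comparison. Much of what a reader needs is already planned: cure at TOC with rescue as failure (SAP 8.1), symptom resolution at FU with rescue as persistence (SAP 8.2.3), continued response at FU (SAP 8.1.1) and the timing of rescue (SAP 7.1.3). Unscheduled examinations can give a sign rating outside the windows. The diary analysis proposed below is a new derivation with limits of its own. All of this stands, and it sets the severity.

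A reader might infer more than the documents support:
- **That the SAP says rescued women are censored.** This is inferred from three sections, and step 5 shows that another reading is open.
- **That rescue censoring is the main distortion.** At the end of the curve, censoring non-resolvers at staggered FU days accounts for more.
- **That the curve favours one arm.** Step 4 gives either sign, and no placebo rescue rate is stated.

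None of this rescues the median. Unscheduled examinations are still visit days, and the zero rule at FU settles the score but not the date.

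**Conclusion.** The point holds, at minor severity. As written, the Kaplan-Meier median cannot distinguish a true median of Day 4 from one of Day 8. At the sponsor's own 50% cure rate it is close to a coin toss between the two visit windows. These results rest on the stated windows and uniform attendance.

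The missing rule for non-resolvers can lift the end of the placebo curve from 51% to about 72% under the assumed 30% late resolution. Rescue handling is ambiguous and, on the likelier reading, overstates resolution, for example 33% instead of 30% at Day 14 with 10% placebo rescue before TOC. That rescue rate is an assumption. No direction of bias in the treatment difference is claimed, and the primary result is unaffected.

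**What to change.** 1. **For speed of relief**, replace the analysis with time to symptom resolution from the daily diary, Day 1 to TOC. The event is the first day with itching, burning and irritation all recorded as 0, and a missing day is not a zero. Treat rescue antifungal or topical vaginal therapy before resolution as a competing event, report cumulative incidence by arm, and censor unrescued, unresolved women at their last diary day.
2. **For signs plus symptoms**, drop the Kaplan-Meier median and curves. Report the proportion resolved at TOC (already planned as clinical cure) and at FU with rescue as non-resolution. Alternatively, use an interval-censored estimator with rescued women held as non-resolved. A visit-day cumulative incidence curve is no substitute: with no rescue it is the same curve and ends at the same 72%.
3. **Separately**, reconcile rescue at the FU visit. Protocol 11.4 calls it early termination, whereas SAP 5.1 has a category of "subjects who completed the study (with need for antifungal treatment at FU visit". This affects the disposition table only.

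The cost is SAP wording and one derivation from diary data already entered in the eCRF. Visits, sample size and the primary analysis do not change. The diary analysis covers symptoms only, stops at TOC and counts a single all-zero day as resolution. The SAP should state these limits.
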